8.2 Dose Modifications for Hematologic Toxicities

Worst Toxicity by CTCAE Grade ^{b, c}	nal-IRI or 5-FU ^e
Grade 2 neutropenia (ANC < 1500 – 1000 cells/mm ³)	100% of previous dose
Grade 3 or 4 neutropenia (ANC ≤ 1000 cells/mm ³) or febrile neutropenia ^a	^{1st} occurrence: Delay treatment ^d until resolved to ≤ Grade 2, then reduce dose to by 25% ^{2nd} occurrence: Delay treatment ^d until resolved to ≤ Grade 2, then reduce dose another 25% (50% of original dose)
≤Grade 2 thrombocytopenia (Grade 2: platelets ≤75,000/mm ³ -50,000/mm ³)	If Grade 2: 100% of previous dose
Grade 3-4 thrombocytopenia: platelets <50,000/mm ³)	If Grade ≥3: ^{1st} occurrence: Delay treatment ^d until resolved to ≤ Grade 2, then reduce dose by 25% ^{2nd} occurrence: Delay treatment ^d until resolved to ≤ Grade 2, then reduce dose another 25% (50% of original dose)

^aConsider the use of G-CSF for patients who experience ≥ Grade 3 neutropenia or febrile neutropenia.

^bAnemia: no changes; transfuse as needed.

^cLymphocytopenia: no changes.

^dFor Grade 3 and worse neutropenia and/or platelets, delay all agents (5FU, leucovorin, nal-IRI and rucaparib) until resolve to ≤ Grade 2.

^eThe dose of the agent (5FU or nal-IRI) that is most likely the cause of the hematologic toxicity, as per investigator's assessment, will be reduced when resuming treatment.

8.21 Recommended dose modification for toxicities *except* ALT/AST/ bilirubin

NCI-CTCAE v4.03 ^a	Dose Interruption	Dose Modification ^b	Dose for Subsequent Cycles
Grade 0 - < 2 Non-hematologic	Treat on time	No change	
Grade 2 Non-hematologic [*]	May be held and/or reduced for toxicities not adequately controlled by concomitant medication and/or supportive care at the discretion of the treating investigator.		If toxicity remains \leq Grade 1, dose re-escalation can be considered at the discretion of the treating investigator.
Non-hematologic Grade \geq 3 (with the exception of electrolyte abnormalities not considered clinically significant by the treating physician)	Delay until \leq Grade 2	Reduce by 1 dose level Permanent discontinuation can be considered at treating investigator's discretion.	If toxicities return to baseline or \leq Grade 1 or \leq Grade 2 severity if not considered a safety risk for the patient, dose re-escalation can be considered at the discretion of the treating investigator.

a. NCI-CTCAE = National Cancer Institute - Common Terminology Criteria for Adverse Events, version 4.03 [REDACTED]

b. Excludes alopecia, non-refractory nausea/vomiting, or diarrhea adequately controlled with systemic antiemetic/antidiarrheal medication administered in standard doses according to institutional guidelines.

*Grade 2 creatinine elevations are likely to be seen due to potent inhibition of MATE1 and MATE2-K by rucaparib. Dose modifications of rucaparib for grade 2 creatinine are not needed unless the treating physician has concerns that other factors may be contributing to creatinine elevations.

8.22 Recommended dose modifications/interruptions for elevations in ALT and/or AST related to rucaparib

NCI-CTCAE v4.03 ^a	Dose Interruption ^b	Dose Modification	Dose for Subsequent Cycles
Grade ≤ 2	Treat on time	No change	
Grade ≥ 3	
 • Treat on time • Monitor liver function tests weekly until resolution to \leq Grade 2 	No change, provided bilirubin is $<$ ULN and alkaline phosphatase is $<$ 3 x ULN.	If toxicity remains and levels do not decline within 2 weeks or they continue to rise, treatment interruption and resolution to \leq Grade 2 is required before rucaparib can be resumed, either at the current dose or a reduced dose.
Grade ≥ 4	
 • Hold rucaparib • Monitor liver function tests weekly until resolution to \leq Grade 2 		Resume with a dose reduction and monitor liver function tests weekly for 3 weeks after restarting.

a. NCI-CTCAE = National Cancer Institute - Common Terminology Criteria for Adverse Events, version 4.03

b. Treatment with rucaparib should be held until the toxicity resolves to \leq CTCAE Grade 2. Twice daily dosing may then be resumed at either the same dose or a lower dose, per investigator discretion. If treatment is resumed at the same dose, and the patient experiences the same toxicity, the dose should be reduced following resolution of the event to \leq CTCAE Grade 2. If the patient continues to experience toxicity, additional dose reduction steps are permitted; however, the investigator should contact ACCRU (see Protocol Resource page) before reducing to 300 mg BID. If a patient continues to experience toxicity despite dose reduction steps to 300 mg BID, or if dosing with rucaparib is interrupted for $>$ 14 consecutive days due to toxicity, treatment should be discontinued, unless otherwise agreed between the investigator and ACCRU.

8.3 Dose Modifications for Non-Hematologic Toxicities Other than grade 3 ALT/AST (follow recommendation by Table 8.22), Fatigue and Grade 3 Anorexia^{a, d}

Worst Toxicity by CTCAE Grade*	na1-IRI	5-FU
Grade 1 diarrhea ^b	Continue same dose	Continue same dose
Grade 1 or 2 including diarrhea (except alopecia, nausea and vomiting)	Withhold na1-IRI then resume once resolved to grade 1 at 100% of previous dose	Withhold 5-FU, then resume once resolved to grade 1 at 100% of previous dose, except for Grade 2 hand foot syndrome, Grade 2 cardiac toxicity, or any grade neurocerebellar toxicity
Grade 3 or 4, including diarrhea ^c (except alopecia, nausea and vomiting)	Withhold na1-IRI then resume once resolved to grade 1 per below: 1 st occurrence: Reduce dose to by 25% 2 nd occurrence: Reduce dose another 25% (50% of original dose)	Withhold 5-FU then resume once resolved to grade 1 per below: 1 st occurrence: Reduce dose by 25% 2 nd occurrence: Reduce dose another 25% (50% of original dose) *except for Grade 3 or 4 hand foot syndrome
Grade 3 or 4 nausea and/or vomiting, despite anti-emetic therapy	Optimize anti-emetic therapy AND reduce dose to 50 mg/m ² , if starting dose is 70 mg/m ² .. If the patient is already receiving 50 mg/m ² , reduce dose to 43 mg/m ² , ^c	Optimize anti-emetic therapy AND reduce dose by 25%; if the patient is already receiving a reduced dose, reduce dose an additional 25% ^e
Grade 2 hand foot syndrome	100% of previous dose	1 st occurrence: Reduce dose by 25% 2 nd occurrence: Reduce dose another 25% (50% of original dose) ^d
Grade 3 or 4 hand foot syndrome	1 st occurrence: Reduce dose to 50 mg/m ² , if starting dose is 70 mg/m ² . 2 nd occurrence: Reduce dose to 43 mg/m ²	Discontinue therapy
Any grade neurocerebellar or ≥ Grade 2 cardiac toxicity	No dose modifications required ^d	Discontinue therapy
Sensory neuropathy	No dose modifications required ^d	No dose modifications required ^d

* Located at [REDACTED]

^a Fatigue and Grade 3 anorexia do not require dose modification.

^b Grade 1 diarrhea: 2-3 stools/day > pretreatment.

^c Grade 2 diarrhea: 4-6 stools/day > pretreatment; Grade 3 diarrhea: 7-9 stools/day > pretreatment; Grade 4 diarrhea: > 10 stools/day > pretreatment.

^d Any toxicity ≥ Grade 2, except anemia and alopecia, can justify a dose reduction if medically indicated.

^e Patients who require more than 2 dose reductions must be withdrawn from the study.

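### Table 8.22: footnote b permits a same-dose rucaparib restart after a grade 4 ALT/AST hold, where the grade 4 row calls for a reduced dose, and no text says which prevails

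*Combined protocol and SAP*

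**What the plan says.** Table 8.22 has three rows, printed as Grade ≤ 2, Grade ≥ 3 and Grade ≥ 4.

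- **Grade ≥ 3 row.** Rucaparib is given on time with weekly liver tests. The dose instruction is "No change, provided bilirubin is" below the upper limit of normal and alkaline phosphatase is below three times it. The last column adds: "If toxicity remains and levels do not decline within 2 weeks or they continue to rise, treatment interruption and resolution to" grade 2 or lower "is required before rucaparib can be resumed, either at the current dose or a reduced dose".
- **Grade ≥ 4 row.** The interruption instruction is "Hold rucaparib", with weekly liver tests until grade 2 or lower. The last column says "Resume with a dose reduction and monitor liver function tests weekly for 3 weeks after restarting".
- **Footnote b**, attached to the header of the dose-interruption column, holds rucaparib until grade 2 or lower and continues: "Twice daily dosing may then be resumed at either the same dose or a lower dose, per investigator discretion". If the same toxicity returns after a same-dose restart, the dose is then reduced. Further steps are allowed, with ACCRU contacted before going to 300 mg BID. Interruption for more than 14 consecutive days means discontinuation unless ACCRU agrees otherwise.

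Section 8.1 gives the rucaparib steps (600 to 500 to 400 mg BID) and allows at most two reductions. Section 8.0 makes the modifications strict for the first two cycles and guidance after that. Section 7.12 sets the recommended rucaparib dose at 600 mg BID.

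**The concern.** The grade 4 row offers one way back onto rucaparib, at a lower dose. Footnote b offers two, the same dose or a lower one, and leaves the choice to the investigator. A reduced restart complies with both texts. A same-dose restart complies with the footnote and breaches the row. Under the footnote, reduction becomes necessary only once the same toxicity has recurred.

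At stake is dosing after a grade 4 hepatic event, and consistency between sites. Section 15.17 lists raised ALT/AST among rucaparib's common toxicities (above 10%), so this table will be consulted. During the first two cycles sites are told to follow the rules strictly, and they cannot do that while two rules differ.

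There is also a lesser problem. As printed, the treat-on-time row (Grade ≥ 3) contains the hold row (Grade ≥ 4).

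**Working it through.** The plan gives no figure to reproduce here. The check is a comparison of texts, followed by the size of the dose gap.

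**1. Restart options after a grade 4 ALT/AST hold**

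| Source | Same dose | Reduced dose |
|---|---|---|
| Table 8.22, grade 4 row | not offered | required |
| Table 8.22, footnote b | allowed | allowed |

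Footnote b hangs on the column that contains the grade 4 hold, so it reaches that hold, and it carries no grade 4 exception. For grade 3, the row itself allows the current or a reduced dose once interruption has been required, so row and footnote agree there.

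**2. Does another text decide it?**

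- *Table 8.21*: no. Its title is "Recommended dose modification for toxicities *except* ALT/AST/ bilirubin".
- *Section 8.1 heading with Table 8.3*: leans to reduction. The heading ties rucaparib modifications to events in Tables 8.2 and 8.3. The title of Table 8.3 carves out only grade 3 ALT/AST, so grade 4 falls in its grade 3 or 4 row, where a first occurrence brings a 25% cut. That table's dose columns cover only nal-IRI and 5-FU, so it states no rucaparib restart dose.
- *Section 13.1*: leans to reduction. Same-dose continuation is for patients without intolerable toxicity; those with unacceptable toxicity may be retreated at a lower dose, at the physician's discretion.
- *Section 7.42*: leans to reduction. Grade 4 or higher ALT is a DLT and the patient continues at the next lower level. It applies only to the Phase I cycle 1 window, and isolated AST rises are not dose-limiting.

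Three texts favour the row. None says that the row overrides the footnote.

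**3. Size of the gap at the recommended dose**

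- Footnote b, same dose: 600 mg × 2 = 1200 mg/day.
- Grade 4 row with the first Section 8.1 step: 500 mg × 2 = 1000 mg/day.
- Difference: (1200 − 1000)/1200 = 200/1200 = 16.7%.
- Patient already at 500 mg BID: (1000 − 800)/1000 = 20%.

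Dosing days per cycle are 10 (days 4–13) + 10 (days 18–27) = 20. Over a cycle that is 24,000 mg against 20,000 mg. This restates one dose step and does not measure harm.

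**4. Reach of the row-label overlap**

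A grade 4 value satisfies both printed labels. A patient who rises from grade 3 to grade 4 on treatment already meets the first row's interruption clause for rising levels. Table 8.3 withholds nal-IRI and 5-FU at grade 4 in any case. Read literally, the overlap matters only for rucaparib when an elevation is first found at grade 4.

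**5. A related inconsistency in footnote b**

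From 600 mg BID, reaching 300 mg BID takes three steps: 600 → 500 → 400 → 300. Section 8.1 allows two, ending at 400 mg BID. The footnote contemplates the third step after contact with ACCRU; Section 8.1 does not.

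**The case against.** The best reply is that the table can be read consistently. Footnote b sits on the interruption column, while the restart dose is set in the last column, which carries no such footnote. The footnote's same-or-lower option closely matches the grade 3 row's own wording, so it may have been written for grade 3 interruptions. A specific row would normally control a general, permissive note, and the texts in step 2 point the same way. The exposed group is also narrow: a grade 4 event, resolved within 14 days, and an investigator who passes over the row's explicit instruction.

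Most of this stands. The grade 4 row is probably what was intended, and a careful site would follow it. But that is inference: the footnote speaks directly about the restart dose, exempts no grade and invokes investigator discretion.

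Three stronger readings are tempting and are not supported.

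- A reader might infer that Table 8.22 is the only text bearing on rucaparib after grade 4 ALT/AST outside the DLT window. The Section 8.1 heading with Table 8.3, and Section 13.1, also bear on it.
- A reader might infer that the overlapping labels amount to an instruction to treat through grade 4. The separate hold row and the title of Table 8.3, which refers only grade 3 ALT/AST to Table 8.22, make the intended meaning plain. A misread sign in the PDF text also cannot be excluded, and the footnote conflict does not depend on it.
- A reader might infer that failing the bilirubin or alkaline phosphatase proviso at grade 3 requires a hold. The row says only when the dose stays unchanged; it never states that interruption follows otherwise.

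**Conclusion.** The conflict between footnote b and the grade 4 row is real and should be corrected. It is a modest safety-wording matter. At the recommended dose it is one dose step: 1200 against 1000 mg/day, 16.7% lower under the row (20% for a patient already at 500 mg BID). The label overlap is a slip. The 300 mg BID step against the two-reduction cap is a further inconsistency, best settled in the same edit.

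This rests on reading footnote b as covering every hold in the column it is attached to, and on the absence of any precedence statement in the documents. The documents give no frequency of grade 4 ALT/AST, so no number of affected patients is claimed. Endpoints, sample size and error rates are unaffected.

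**What to change.** Amend Table 8.22 in three places.

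1. Relabel the treat-on-time row Grade 3 and the hold row Grade 4.
2. Replace the second sentence of footnote b with wording to this effect: *After interruption for a grade 3 event, rucaparib may restart at the current or a lower dose as the investigator judges; after a grade 4 event, it restarts only at a reduced dose under Section 8.1.*
3. Reconcile the step to 300 mg BID with Section 8.1's cap, for example by stating that any reduction beyond two needs ACCRU agreement and that rucaparib is otherwise discontinued. This also settles what happens to a patient who has grade 4 at 400 mg BID after two reductions.

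Keep the existing rules on recurrence and on interruption beyond 14 days. Do not add a list of hold triggers that includes the bilirubin and alkaline phosphatase proviso; that would be a new clinical rule.

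The cost is an amendment to two row labels and a few footnote sentences. Investigators lose the option of a same-dose restart after grade 4. Visits, sample size and analyses do not change.

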8.0 Dosage Modification Based on Adverse Events

Strictly follow the modifications in this table for the first **two** cycles, until individual treatment tolerance can be ascertained. Thereafter, these modifications should be regarded as guidelines to produce mild-to-moderate, but not debilitating, side effects. If multiple adverse events are seen, administer dose based on greatest reduction required for any single adverse event observed. Reductions or increases apply to treatment given in the preceding cycle and are based on adverse events observed since the prior dose.

ALERT: *ADR reporting may be required for some adverse events (See Section 10)*

8.1 Dose Modifications for Rucaparib (Based on Adverse Events in Tables 8.2 and 8.3)

Starting Dose Level	1 st Dose Modification	2 nd Dose Modification
600 mg BID	500 mg BID	400 mg BID
400 mg BID	300 mg BID	200 mg BID
300 mg BID	200 mg BID	300 mg QD
200 mg BID	300 mg QD	200 mg QD

NOTE: No more than two dose reductions are allowed.

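### In cycles 1–2 the nal-IRI and 5-FU rule for raised ALT/AST requires a hold at grade 2 and at grade 4 but none at the onset of grade 3

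*Combined protocol and SAP*

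**What the plan says.** Section 8.0 opens with "Strictly follow the modifications in this table for the first" two cycles; after that the modifications become guidelines. It adds that changes "are based on adverse events observed since the prior dose".

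Three parts of Section 8 then bear on ALT/AST:

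- **Table 8.3** has two drug columns, nal-IRI and 5-FU. Its heading covers non-hematologic toxicities "Other than grade 3 ALT/AST (follow recommendation by Table 8.22), Fatigue and Grade 3 Anorexia". The row for grades 1 and 2 excepts only alopecia, nausea and vomiting, and says to withhold each infusion, "then resume once resolved to grade 1 at 100% of previous dose". The row for grades 3 and 4 has the same exceptions and says "Withhold 5-FU then resume once resolved to grade 1 per below", with a parallel entry for nal-IRI. The steps are 25% less at first occurrence and 50% of the original dose at second. Footnote d to the heading allows a dose reduction for nearly any toxicity of grade 2 or above if medically indicated.
- **Table 8.22** is titled "Recommended dose modifications/interruptions for elevations in ALT and/or AST related to rucaparib". At grade 2 or lower it keeps treatment on schedule, unchanged. At grade 3 it also keeps treatment on schedule, and its dose entry reads "No change, provided bilirubin is" below the upper limit of normal (ULN) and alkaline phosphatase is below 3 × ULN. It adds weekly liver tests, and an interruption if levels have not declined within 2 weeks or keep rising. At grade 4 it holds rucaparib.
- **Section 8.1** is titled "Dose Modifications for Rucaparib (Based on Adverse Events in Tables 8.2 and 8.3)", although Table 8.3 has no rucaparib column.

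**The concern.** A toxicity rule should not become less strict as the toxicity gets worse. Read literally, Table 8.3 withholds both infusions from a patient whose ALT is at grade 2 on infusion day. For a patient at grade 3 that day, it hands the decision to a table that states no infusion hold. At grade 4 the hold returns.

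Two things are at stake. Sites could handle the same grade 3 patient differently during the only period when the rules are binding. And a grade 3 rise attributed to nal-IRI, 5-FU or liver metastases falls outside the title of Table 8.22 as well as outside Table 8.3. The situation is not remote: Section 15.17 lists increased ALT/AST among the common (more than 10%) rucaparib toxicities. Section 10.521 has both graded at each evaluation, and Section 7.2 requires evaluation at least every 14 days.

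**Working it through.** The plan gives no figure to reproduce. The check is to read Section 8 grade by grade and then put the recommended dose through it. Section 7.12 names that dose as DL2-A: nal-IRI 50 mg/m² and 5-FU 2400 mg/m².

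Arithmetic for the Table 8.3 reductions:

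- First occurrence: 50 × 0.75 = 37.5 mg/m² nal-IRI; 2400 × 0.75 = 1800 mg/m² 5-FU.
- Second occurrence (50% of original): 50 × 0.5 = 25 mg/m²; 2400 × 0.5 = 1200 mg/m².

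The two tables side by side, for an elevation still at the stated grade on infusion day:

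| ALT/AST grade | Table 8.3 (nal-IRI / 5-FU) | Table 8.22 |
|---|---|---|
| 2 | hold until grade 1, then 50 / 2400 | on schedule, no change |
| 3 | removed by the heading | on schedule; no change if bilirubin < ULN and alkaline phosphatase < 3 × ULN; weekly tests; interruption if not declining within 2 weeks or still rising |
| 4 | hold until grade 1, then 37.5 / 1800 (first occurrence) | hold rucaparib; weekly tests; resume at a reduced dose |

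The unresolved status matters. A patient whose grade 2 value is back to grade 1 by infusion day loses nothing, because the row then resumes at full dose. Table 8.22 labels its last two rows as grade 3 or above and grade 4 or above; I take the first of these as grade 3 only.

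Grade 3 then has three possible readings for the next infusion:

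1. Table 8.22 governs the infusions and both laboratory conditions are met: 50 / 2400 on time, with the interruption clause applying later. On this reading, the row for grade 2 or lower in Table 8.22 contradicts the Table 8.3 hold at grade 2. No onset action is given if a laboratory condition fails.
2. Table 8.22 covers rucaparib only: no infusion action is required. Footnote d permits a reduction.
3. The heading was meant to exempt only rucaparib, as the title of Section 8.1 hints: hold until grade 1, then 37.5 / 1800. The heading does not say this; it takes grade 3 out of the whole table.

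Between readings 1 and 3 the resumption dose differs by 50 − 37.5 = 12.5 mg/m² and 2400 − 1800 = 600 mg/m², which is 25% of each drug, plus the delay.

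Infusions exposed in the binding period: 2 cycles × 2 infusion days = 4. The first (cycle 1 day 1) precedes any treatment, so 4 − 1 = 3 are exposed.

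Other rules that might supply the missing hold:

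- Section 8.21 excludes ALT, AST and bilirubin by its title.
- Footnote d of Table 8.3 permits a reduction but does not require a hold.
- The DLT interruption in Section 7.42 concerns cycle 1 of dose escalation. Its ALT-specific criterion starts at grade 4. A catch-all row for other grade 3 events exists, with exceptions. Since the Phase I dose is already chosen, none of this helps Phase Ib or Phase II patients.

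**The case against.** The strongest reply is that grade 3 is not unguarded and that the grade 3 leniency may be deliberate. Table 8.22 requires weekly liver tests. It also requires an interruption for persistent or rising values, and that clause names rucaparib only when it describes resumption. The two-week limit equals one infusion interval, and footnote d leaves room to reduce. Elsewhere the protocol tolerates transaminase rises: the ALT-specific DLT begins at grade 4 (Section 7.421), and Section 15.298 describes enzyme elevations with nal-IRI as transient and needing no intervention. If Table 8.22 is taken as the whole rule, its own sequence is orderly: on schedule, on schedule with conditions, hold. The anomaly is then the generic grade 2 hold in Table 8.3, which costs a delay at full dose.

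Most of this stands. A reader might infer that the plan drops liver protection at grade 3. The documents do not support that, because of the safeguards just listed. What survives is that the two tables, followed as written, cannot both be right about the infusions, and nothing says which one yields.

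A reader might also infer that footnote b of Table 8.22, which speaks of holding rucaparib until grade 2 or lower, flatly contradicts the on-schedule entry at grade 3. It reads more naturally as instructions for managing a hold once one has been triggered. That is an ambiguity, not a firm contradiction.

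**Conclusion.** The concern holds as an inconsistency between two dosing tables. In the binding cycles, a required infusion hold is stated at grades 2 and 4 and not at the onset of grade 3. If Table 8.22 governs the infusions, it conflicts with Table 8.3 at grade 2. If it covers rucaparib only, grade 3 has no required infusion action. Either way the rule needs correcting, since following it literally gives an action that is out of order with severity.

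For one grade 3 patient the text can be read as anything from full dose on time to a hold followed by 25% less of each infused drug. Three of the four infusions in cycles 1–2 are exposed. This rests on taking the reference to a table in Section 8.0 as meaning all of Section 8, which it introduces.

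The documents do not settle which grade is mis-specified. The number of patients affected and the dose lost cannot be estimated from them, and no endpoint or decision rule is shown to change. The case for amending is that the rule is wrong as written and cheap to repair.

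**What to change.** Amend the heading of Table 8.3 so that the nal-IRI and 5-FU action never becomes less strict as ALT/AST grade rises. Two repairs are coherent, and the study team should choose on clinical grounds:

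- **(A)** Limit the exemption to rucaparib: Table 8.3 applies except for rucaparib dosing at grade 3 ALT/AST, which follows Table 8.22. The infusions then fall in the row for grades 3 and 4. The sequence becomes hold and resume at 100%, hold and resume 25% lower, hold and resume 25% lower.
- **(B)** Extend the exemption to grades 2 and 3, and state in Table 8.22 that it governs nal-IRI and 5-FU at those grades whatever the attribution. Add the action when the bilirubin or alkaline phosphatase condition is not met. The sequence becomes on schedule, on schedule with conditions, hold.

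In either case, reword footnote b of Table 8.22 so that it plainly applies once a hold has been triggered. The cost is a wording amendment to two tables and one footnote, with no added data or patients.

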The recommended dose determined by phase I dose escalation is dose level 2-A (DL2-A in section 7.11)

Agent	Dose	Route	Day
nal-IRI	50 mg/m ² (Recommended Dose Determined by Phase I Dose Escalation)	Intravenous over 90 minutes	Days 1 and 15
5-FU	2400 mg/m ²	Intravenous over 46 hours	Day 1 and 15
Rucaparib	600 mg (Recommended Dose Determined by Phase I Dose Escalation)	Oral	Twice daily on Days 4-13 and days 18-27 (Recommended schedule determined by phase I dose escalation)

7.13 Phase II (Phase II study at recommended dose level determined by the Phase I portion)

Agent	Dose	Route	Day
nal-IRI	Recommended Dose Determined by Phase I Dose Escalation	Intravenous over 90 minutes	Days 1 and 15
5-FU	2400 mg/m ²	Intravenous over 46 hours	Days 1 and 15
Rucaparib	Recommended Dose Determined by Phase I Dose Escalation	Oral	Twice daily on days as determined by Phase I administration schedule

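### At the 50 mg/m² nal-IRI start used in Phase Ib and carried to Phase II, Table 8.3 gives conflicting or missing nal-IRI steps for hand foot syndrome and repeat vomiting

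*Combined protocol and SAP*

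**What the plan says.** **Starting dose.** Section 7.12 states: "The recommended dose determined by phase I dose escalation is dose level 2-A (DL2-A in section 7.11"). Its table lists nal-IRI 50 mg/m². Section 7.13 gives no number for Phase II but is headed "Phase II study at recommended dose level determined by the Phase I portion".

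**How binding the tables are.** Section 8.0 opens with "Strictly follow the modifications in this table for the first" two cycles; after that the entries are guidelines. When several adverse events are seen, the greatest single reduction applies.

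**Percentage entries.** Table 8.2 cuts the responsible agent by 25% at the first grade 3/4 neutropenia or thrombocytopenia. At the second, treatment waits until "resolved to ≤ Grade 2, then reduce dose another 25% (50% of original dose"). The general grade 3/4 row of Table 8.3 uses the same two steps for nal-IRI. It excludes alopecia, nausea and vomiting. A further exception, "except for Grade 3 or 4 hand foot syndrome", is printed in the 5-FU cell only.

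**Fixed entries for nal-IRI in Table 8.3.**
- Grade 3/4 nausea or vomiting: "Optimize anti-emetic therapy AND reduce dose to 50 mg/m"² for a 70 mg/m² start. A second branch begins "If the patient is already receiving 50 mg/m"² and leads to 43. No further step follows.
- Grade 3/4 hand foot syndrome: the first occurrence goes to 50, on condition of a 70 mg/m² start. The second goes to 43, with no condition on the starting or current dose.

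**The concern.** The two fixed-value rows descend from a 70 mg/m² start, while the neighbouring entries are percentages of whatever dose was started. At 50 mg/m² the two scales no longer line up. Sites told to apply the table strictly could give different nal-IRI doses for the same event, or find no entry at all. In one sequence, an entry labelled a reduction would raise the dose after a grade 3/4 toxicity. These are operative dosing instructions, so patient safety is directly involved. Tolerability at the recommended dose is also part of the Phase Ib primary aim (Section 2.21), and exposure would then depend partly on which row a site happened to read.

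**Working it through.** **Check of the plan's own figure.** Two cuts of 25% of the original dose give 1 − 0.25 − 0.25 = 0.50, which matches the stated 50% of original. Compounding would give 0.75 × 0.75 = 0.5625, which does not match. The percentage steps are therefore fractions of the starting dose.

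**Inputs.** Start 50 mg/m² (7.12). Percentage steps 25%, then 50% of original (8.2 and the general row of 8.3). Fixed steps 50 and 43 mg/m² (nausea/vomiting and hand foot syndrome rows of 8.3).

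**Percentage scale from 50.** First cut 50 × 0.75 = 37.5; second 50 × 0.50 = 25.

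**(a) Grade 3/4 hand foot syndrome, 50 mg/m² start**

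| Occurrence | Own row | General grade 3/4 row |
|---|---|---|
| First | no step, so 50 unchanged | 37.5 |
| Second | 43 | 25 |

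At the second occurrence, 43 / 25 = 1.72, so one reading gives 72% more drug than the other. The conflict is not peculiar to 50: from a 70 mg/m² start the pairs are 50 against 52.5 (70 × 0.75) and 43 against 35 (70 × 0.50). What is peculiar to 50 is that the event's own row has no first step.

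**(b) A reduction that raises the dose.** A 50 mg/m² starter cut once by 25% is at 37.5. The second-occurrence hand foot syndrome entry then reads 43, and 43 / 37.5 = 1.147, or about +15%. Two routes lead there within two reductions:
- A 25% cut for neutropenia attributed to nal-IRI, then a first hand foot syndrome event with no step in its own row, then a second event.
- The general row used at the first hand foot syndrome event because the specific row is silent, then the specific row at the second.

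From a 70 mg/m² start, one 25% cut leaves 52.5, and the fixed entries are still reductions: 50 / 52.5 = 0.952 and 43 / 52.5 = 0.819.

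**(c) Grade 3/4 nausea or vomiting, 50 mg/m² start.** The first event at 50 goes to 43, a cut of 1 − 43/50 = 14%. A patient already at 43 (second episode) or at 37.5 (after an earlier percentage cut) matches neither branch, and the general row excludes nausea and vomiting. The adjacent 5-FU cell does provide for a patient already on a reduced dose; the nal-IRI cell does not.

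**The case against.** **The specific row governs.** A reader would normally apply the hand foot syndrome row over the general one, and the exception in the 5-FU cell may have been meant for the whole row. If so, the two-dose conflict goes, but the first occurrence at 50 mg/m² has no step. If the general row governs, the step exists and the specific row contradicts it. These are alternative readings of one defect, not two defects, and neither is clean.

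**The increase is strained.** Section 8.0 ties changes to the treatment given in the preceding cycle, and an entry that says to reduce cannot sensibly raise that dose. The route through neutropenia needs nal-IRI to be judged the responsible agent (8.2, footnote e), followed by two grade 3/4 hand foot syndrome episodes, although 5-FU is discontinued at the first. Strict adherence covers only two cycles, or four infusions. All of this stands: it is a fault of the literal wording in an unusual sequence.

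**Other text fills the gaps.** The greatest-reduction rule addresses several events seen together, not two rows for one event, a later event, or a row with no entry. Footnote d of Table 8.3 permits a discretionary reduction but gives no dose. Table 8.21 lowers by one level for grade 3 or worse non-hematologic events, but it names no agent and gives no nal-IRI value.

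**Hand foot syndrome is rare.** Section 15.37 lists it below 1% for 5-FU and Section 15.198 calls it rare for rucaparib. This stands. It does not touch (c): Section 15.27 lists vomiting among the most common reactions to nal-IRI with 5-FU and leucovorin, and neutropenia among the most common grade 3/4 laboratory abnormalities.

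**Conclusion.** The nal-IRI entries in Table 8.3 are inconsistent for a 50 mg/m² start. A first grade 3/4 hand foot syndrome event gives 50 or 37.5 mg/m² and a second 43 or 25, depending on the row read. A patient at 37.5 can be sent literally to 43, about 15% up, in a particular sequence. Repeat nausea or vomiting at 43, or any grade 3/4 episode at 37.5, has no nal-IRI entry. This last gap is the likeliest to arise in practice.

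Three stronger readings are not supported:
- **That these rows ignore a 50 mg/m² patient altogether.** The nausea/vomiting row has a branch for a patient on 50.
- **That a patient at 35 mg/m² would be sent to 50.** That needs a 70 mg/m² start and two earlier cuts. A third reduction then appears to require withdrawal under footnote e. The superscript on that nal-IRI cell prints as c, so whether footnote e applies there is not certain.
- **That all patients are affected.** The 40 Phase Ib and up to 52 Phase II patients (92 in all) are those governed by the table, not expected events. The documents give no hand foot syndrome rate for the combination. If the below-1% figure for 5-FU is assumed to hold, the expected number is under 0.01 × 92 = 0.92.

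The conclusion assumes that Phase II starts at the DL2-A dose, as Section 7.13 implies. It does not affect the primary endpoint definition or the decision rule.

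**What to change.** In the next amendment, the sponsor should reconcile Sections 7.12 and 7.13, the instructions in 8.0, Table 8.2, and the general grade 3/4, nausea/vomiting and hand foot syndrome rows of Table 8.3. The result should meet three checks:

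1. Each event leads to exactly one nal-IRI instruction for a 50 mg/m² start.
2. Patients whose nal-IRI dose has already been reduced also have an instruction for each event.
3. No entry labelled a reduction yields a dose above the last one given.

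Which row governs, whether toxicity-specific scales are kept, and all dose values are for the sponsor to decide; none is proposed here. The cost is table wording and a memo to sites. No new procedures, data or patients are needed.
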